### 14.4.2. Disposition of Study Subjects

Subject disposition of will be summarized using categorical summaries. The number and percent of patients who were enrolled in the study, excluded from the study, included in the safety, and effectiveness analysis set, completed the study, and prematurely discontinued from the study will be presented. Patients who prematurely discontinued will be summarized by number and percentage by primary reason for discontinuation.

A listing of subject disposition will be generated as well as flow diagrams.

### 14.4.3. Demographic and Baseline Characteristics

All demographic and baseline characteristics will be summarized using categorical and continuous summaries, as appropriate, for all the safety analysis set.

A listing of subject demographic and baseline characteristics will be generated.

#### 14.4.4. Analysis for Primary Endpoint

Acute procedural success will be summarized using categorical summaries for the effectiveness analysis set.

A listing of the primary endpoint will be provided.

#### 14.4.5. Analyses of Additional Endpoints

All analyses of additional endpoints will use the effectiveness analysis set.

Procedural parameters (Total procedure time, Mapping time, PV ablation time, Total ablation time, RF application time, and Total Fluoroscopy time) will be analyzed using the safety analysis set using continuous summaries.

Procedural data measures (Catheter ablations outside the PV area, PVI achieved with QMODE+ only among all targeted veins and by subject, PVI achieved with combined use of QMODE+ and QMODE among all targeted veins and by subject, Need for ablation of acute PV reconnection (touch-up) among all targeted veins and by subject, Total number of RF applications, % QMODE+ applications and % QMODE applications, Anatomical location of touch-up applications using the QDOT catheter, and Confirmation of RF energy delivery from nGEN log files) will be summarized using categorical summaries.

Procedural details will be summarized as follows. Temperature, power, contact force, and impedance during RF application will be summarized using continuous summaries. Anatomical segment location per RF application will be summarized using categorical summaries.

Listings of additional endpoints will be generated.

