### 14.4. Analyses to be conducted

### 14.4.1. General Conventions

Standard descriptive summaries for continuous data include the number of observations with data, mean, standard deviation (SD), median, minimum, and maximum values. The mean and median will be rounded to one decimal place greater than in the raw data where applicable; the standard deviation will be rounded to two decimal places greater than in the raw data where applicable. In cases where this is not applicable (e.g., average time spent), the mean will be rounded to one decimal place; the standard deviation to two decimal places; the minimum and maximum to the nearest whole number. These will be referred to as "continuous summaries" in this document.

For categorical data, the count and percent will be provided. Percentages will be based on the number of subjects without missing data. For adverse event and device effects data, percentages will be based on the number of subjects in the analysis population being used in the analysis. When count data are presented, the percentage for zero counts will be suppressed in order to draw attention to the non-zero counts. Frequency counts will be presented as whole numbers and

percentages will be rounded to one decimal place. This will be referred to as "categorical summaries" in this document.

Adverse events (AE) tables will be sorted by decreasing frequency of events, unless otherwise specified.

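### Section 14.4.5 gives the number of RF applications and the QMODE+ and QMODE percentages a count-and-percent summary, so no mean, median or spread is specified and the unit of the mode percentages is not stated

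*Combined protocol and SAP*

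**What the plan says.** The statistical section of the combined protocol and SAP is purely descriptive: section 14.1 rules out formal inference and section 14.3 gives no power calculation. The choice of summary statistic is therefore the analysis.

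Section 14.4.1 defines two types of summary.

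- Continuous: "Standard descriptive summaries for continuous data include the number of observations with data, mean, standard deviation (SD), median, minimum, and maximum values".
- Categorical: "For categorical data, the count and percent will be provided". The base is then given: "Percentages will be based on the number of subjects without missing data". An exception is made only for adverse event and device effect data, which use the analysis population.

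Section 14.4.5 allocates the additional endpoints to these types.

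- Six times get continuous summaries: "Procedural parameters (Total procedure time, Mapping time, PV ablation time, Total ablation time, RF application time, and Total Fluoroscopy time) will be analyzed" in that way.
- So do the RF delivery readings: "Temperature, power, contact force, and impedance during RF application will be summarized using continuous summaries".
- A third list contains "Total number of RF applications, % QMODE+ applications and % QMODE applications". It ends: "Confirmation of RF energy delivery from nGEN log files) will be summarized using categorical summaries". No item in the list is exempted.

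Section 14.4.5 closes with "Listings of additional endpoints will be generated". Section 3.2.2 names the three measures as additional endpoints. Section 8.2.3 has the mode recorded for each lesion and the number of applications recorded in total and by mode.

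**The concern.** A number of applications per procedure, and the percentage of them given in one mode, are numeric variables. The summary assigned to them is meant for categories. Taken literally, the final tables would show no typical value and no between-subject variation for either.

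This matters because section 2 sets out to evaluate workflow, with QMODE+ as the primary mode for isolation and QMODE as the fallback. The number of applications a procedure took, and how much of it was done in QMODE+, describe directly how that strategy worked in practice.

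The text also leaves the programmer to choose the unit. Neighbouring items state theirs: the isolation and touch-up items are reported by targeted vein and by subject, and anatomical segment is reported per RF application. The three measures here name none.

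**Working it through.** The plan gives no figure to reproduce. The check is first textual, then arithmetic on assumed inputs, because the documents give no application counts or mode shares.

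**Step 1. Which summary applies.** The three measures sit in the list that section 14.4.5 sends to categorical summaries. Section 14.4.1 reserves the mean, SD, median, minimum and maximum for continuous summaries. No other section assigns these measures a continuous summary.

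**Step 2. By-subject reading.** The subject base in section 14.4.1 points to a frequency table of the observed values. Assume that applications per subject are lognormal with median 80 and log-SD 0.35. Simulation gives on average 26.0 distinct values among 30 subjects and 39.4 among 50. A row holding one subject shows 1/30 = 3.3% or 1/50 = 2.0%. Such a table is nearly a listing.

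**Step 3. Pooled reading, not stated in the plan.** Let subject i have n_i applications and QMODE+ share p_i.

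- Pooled share = Σ n_i p_i / Σ n_i
- Mean of subject shares = Σ p_i / N
- Pooled minus mean = Cov(n, p) / mean(n)

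The gap is therefore zero when case length and mode share are uncorrelated, and the pooled figure is the lower one only if longer cases use less QMODE+.

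Assume ordinary cases have 80 applications at 95% QMODE+, and that three cases are longer with a lower share. Worked example, N = 30, long cases with 160 applications at 50%:

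- Pooled = (27×80×0.95 + 3×160×0.50) / (27×80 + 3×160) = 2,292 / 2,640 = 86.8%
- Mean = (27×0.95 + 3×0.50) / 30 = 90.5%
- Gap = 3.7 points; the median subject share is 95.0%

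| N | Three long cases | Their share of applications | Pooled | Per-subject mean | Gap (points) |
|---|---|---|---|---|---|
| 30 | 120 applications, 80% | 14.3% | 92.9% | 93.5% | 0.6 |
| 30 | 160 applications, 50% | 18.2% | 86.8% | 90.5% | 3.7 |
| 30 | 240 applications, 20% | 25.0% | 76.25% | 87.5% | 11.25 |
| 50 | 120 applications, 80% | 8.7% | 93.7% | 94.1% | 0.4 |
| 50 | 160 applications, 50% | 11.3% | 89.9% | 92.3% | 2.4 |
| 50 | 240 applications, 20% | 16.1% | 82.9% | 90.5% | 7.6 |

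The gap depends on how many such cases are assumed. Five of 30 at 240 applications and 20% would give 66.9% against 82.5%, a gap of 15.6 points.

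**Step 4. Smoother assumptions.** Now take lognormal counts (median 80, log-SD 0.4) and subject shares that are normal on the logit scale (mean 2.5, SD 1). The average gap is 0.0 points at correlation 0, 1.7 (N = 30) to 1.8 (N = 50) at −0.5, and 2.9 at −0.8. The three longest cases hold about 18% of applications at N = 30 and 12% at N = 50.

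**The case against.** The strongest defence is that, per application, mode is a two-level category. Section 8.2.3 records it that way, and section 3.2.2 lists the total and the two percentages as one item. A grand total split into QMODE+ and QMODE is then naturally a count and percent, and it is a legitimate figure. This stands as a reason to call the unit unclear. It does not close the gap: the reading conflicts with the subject base in section 14.4.1, and it still gives no between-subject spread.

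The consequences are also limited. The planned listings and the per-lesion mode data let anyone recover the per-subject values, so no information is lost. A listing is not a summary, however.

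A reader might infer three stronger claims, none of which the documents support.

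- *Pooled percentages will be driven by a few long cases.* The plan never says that applications are pooled, and its stated base is subjects.
- *Difficult cases would dominate a pooled figure.* Under the three-case assumptions above, the long cases hold 8.7% to 25.0% of applications. They carry extra weight, but they are not a majority, and the effect vanishes if length and mode share are unrelated.
- *The main workflow measures lack centre and spread.* These are additional endpoints. The six procedural times and the temperature, power, contact force and impedance readings do get continuous summaries.

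**Conclusion.** The point holds in a limited form. Section 14.4.5 assigns three numeric additional endpoints a summary that does not fit them, and it leaves the unit of the mode percentages undefined. This follows from the text alone and needs no assumption.

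The size of any pooling effect is conditional. It applies only if applications are pooled, and with three long cases it runs from about 0 to 11 points on assumed counts and shares. The upper end needs those cases to be both three times as long and far lower in QMODE+ use.

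The primary endpoint is binary and suits a count and percent. That analysis, the sample size of 30 to 50 and the time and RF-parameter summaries are unaffected. This is a reporting correction that should be made before database lock; it does not threaten the study's conclusions.

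**What to change.** In section 14.4.5, take the total number of RF applications, % QMODE+ and % QMODE out of the categorical list. State that each is computed per subject and reported with continuous summaries: n, mean, SD, median, minimum and maximum. Name the subject as the unit and define each percentage as that subject's applications in the mode divided by that subject's total applications. If an application-level count and percent pooled over subjects is also wanted, keep it as a secondary line labelled as pooled, with applications as its base.

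The cost is a short change to the text of section 14.4.5 and a small amount of extra table programming. The data are already collected under section 8.2.3.

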### 14.4.6. Analyses of Secondary Safety Endpoints

Secondary safety endpoints will be analyzed using the safety analysis population.

An adverse event (AE) is an event recorded on the Adverse Event CRF page with an onset on or after the study ablation procedure. AEs with onset prior to this date that worsen in severity (i.e., increases in severity) after a subject has signed informed consent OR have a missing onset date are also considered an AE. AEs will be summarized both by subject and event. If a subject has multiple occurrences of an AE, for the by-subject summary only a single occurrence will be counted and for the by-event summary each event will be counted.

The overall incidence of AEs will be summarized by:

- Any adverse event;
- Serious adverse event;
- Non-serious adverse event;
- Device-related adverse event (defined as unlikely, possible, probable or having a causal relationship with the device);
- Serious device-related adverse event;
- Unanticipated device-related adverse event;
- Serious unanticipated device-related adverse event;
- Procedure-related adverse event (defined as unlikely, possible, probable or having a causal relationship with the procedure);
- Adverse events leading to discontinuation.

Serious AEs (SAE) and Non-Serious AEs (NSAE) will be summarized separately by overall incidence and adverse event term using categorical summaries.

An adverse device effect (ADE) is any event recorded to have led to an AE on the Investigational device deficiency CRF.

ADEs will be summarized by overall incidence, ADEs leading to an AE, ADEs leading to an SADE and unanticipated SADE (USADE), device, and time point during the procedure using categorical summaries.

Serious Adverse ADEs (SADE) will be summarized by overall incidence, SADEs leading to an AE, SADEs leading to a USADE, device, and time point during the procedure using categorical summaries.

ADEs, SADEs, and USADEs will be summarized by overall incidence and by adverse event term using categorical summaries in separate tables.

Listings of adverse events and device effects will be generated as well as device deficiencies.

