## 8. Study Schedule

### 8.1. Screening and Informed Consent

All patients considered for RF ablation procedure for drug refractory recurrent symptomatic AF should be evaluated by the investigator or designated member of the research team for study eligibility per the protocol inclusion and exclusion criteria.

The study investigator or designated member of the research team will obtain written informed consent from the subject. The patient informed consent procedure must be done within 60 days before the actual study procedure takes place. The background of the proposed study and the potential benefits and risks of the study should be explained to the subject. The subject must sign the consent form prior to any study-specific exams or tests are provided to them that fall outside of the standard of care. The consent form used must have prior approval from the regulatory authorities (as applicable) and study site's Ethics Committee. Failure to obtain informed consent renders the subject ineligible for participation in the study.

The investigator and/or designee must also clearly document the process of obtaining informed consent in the subject's source documents. The voluntary process of informed consent confirms the subject's willingness to participate in the study. It's the investigator's responsibility to ensure that the informed consent process is performed in accordance with ICH-GCP and with applicable local and federal regulations. If new information becomes available that can significantly affect a subject's future health and/or medical care, this information shall be provided to the subject(s) affected in written form. If relevant, all affected subjects shall be asked to confirm their continuing informed consent in writing by dating and signing an amended ICF.

Each subject screened for enrollment in the clinical study who signs the patient informed consent form will be enrolled into the study. No subject should undergo any clinical investigation specific tests or examinations that fall outside the standard of care without first signing the patient informed consent form for this clinical investigation.

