### 8.5. Schedule of Events Table

This table displays the required schedule for subject treatments and evaluations. Subjects should undergo procedure within 60 days of signing informed consent.

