#### Table 4. Summary of Subject Assessments

Assessments	Pre- ablation	Procedure	Pre- discharge	7D (D6-10)	M3 (D76-104)
Clinic visit	•	•			• 
Phone Call				• 	
Patient Informed Consent 	•				
Demographics 	•				
Medical/AF history	•			•	•
Cardiac and Anticoagulation Medications	•		•	•	•
Ablation Assessment		•			
ECG			• 	• 	● 
Pregnancy Test	• 				
LA thrombus detection	• 				
Adverse events/Device Deficiency 	•	٠	•	٠	•
AF recurrences			•	•	•

1. May be conducted as a clinic visit (ECG performed if Clinic visit) or a telehealth visit.

2. To be completed within 48 hours prior to ablation procedure

3. In all women of childbearing age and potential. To be completed within one week prior to ablation procedure.

4. Device Deficiency to be collected at ablation and pre-discharge

5. If completed at the investigator's discretion.

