## 9.3. Time Period and Frequency for Event Assessment and Follow-up

The investigator, or designated individual, will record all reportable events with start dates occurring any time after informed consent is obtained. At each study visit, the investigator will inquire about the occurrence of AE/SAEs since the last visit.

All AE/SAEs need to be followed until the event is resolved (with or without sequelae). The medical monitor or designee of this clinical investigation will decide if more follow up information is needed in case the event is not resolved at study completion. All required treatments and outcomes of the (S)AE must be recorded in the eCRF. Additional documentation may be requested by the Sponsor or designee, including but not limited to, a written subject narrative detailing the clinical course of the AE/incident, a copy of any correspondence with the local REB, hospital records, death certificate and autopsy report if available. The local CHU will collect the resolution information of any reported SAEs.

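### Section 14.4.6 counts new AEs from ablation but worsening AEs from consent, so pre-ablation events with the same timing are treated differently in the safety tables

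*Combined protocol and SAP*

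**What the plan says.** Section 14.4.6 (Analyses of Secondary Safety Endpoints) sets the AE definition for the tables in two sentences.

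- Onset: "An adverse event (AE) is an event recorded on the Adverse Event CRF page with an onset on or after the study ablation procedure".
- Earlier onset: also counted are "AEs with onset prior to this date that worsen in severity (i.e., increases in severity) after a subject has signed informed consent".
- Missing date: the same sentence continues "OR have a missing onset date are also considered an AE".

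On the interval between consent and ablation:

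- Section 8.1: "The patient informed consent procedure must be done within 60 days before the actual study procedure takes place".
- Section 8.5: "Subjects should undergo procedure within 60 days of signing informed consent". Section 8.2.1 and the line above Table 1 also use 60 days for pre-ablation assessments.
- Footnote 2 of Tables 1 and 4, which is attached to the informed consent row, reads "2. To be completed within 48 hours prior to ablation procedure".

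On collection, Section 9.3 has the investigator "record all reportable events with start dates occurring any time after informed consent is obtained". Sections 8.2.1 and 9.4.1 also start collection at consent. Section 9.1.1 treats deterioration of a baseline condition at any point in the study as an AE. Section 14.4.1 bases AE percentages on all subjects in the analysis population. Section 14.2 restricts the Safety Analysis Set to subjects in whom the investigational device was inserted.

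**The concern.** The two parts of one definition start at different times. Between consent and ablation no study catheter has been inserted and no study energy delivered. Within that window, whether an event enters the tables depends on whether it worsened, and not on when it happened or how serious it was. The resulting counts describe neither the period after ablation nor the period after consent.

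This matters because the study is purely descriptive (Section 14.1) and Section 1.2.1 names acute safety as a main objective. With no test or threshold, the counting rule itself determines the reported AE rates. A reader of the any-AE or serious-AE row could not tell which events preceded the procedure, because no part of Section 14.4.6 splits the tables at ablation.

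**Working it through.** The documents give no figure to reproduce, so the check applies the rule to every possible timing and then gives a scale.

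**Step 1. The rule applied to each timing**

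| Case | Onset | Worsening | In the AE tables? |
|---|---|---|---|
| a | before consent | between consent and ablation | yes |
| b | between consent and ablation | none | no |
| c | between consent and ablation | before ablation | yes |
| d | before ablation | after ablation | yes |
| e | at or after ablation | any | yes |
| f | date missing | any | yes |

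Cases a, b and c can all lie wholly before ablation, yet a and c count and b does not. Case f is a second route by which a pre-ablation event can be counted.

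**Step 2. Comparison with the collection rules**

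Sections 8.2.1, 9.1.1, 9.3 and 9.4.1 all run from consent. The worsening part of Section 14.4.6 agrees with them. The onset part does not.

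**Step 3. Effect of one subject on a by-subject rate**

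The input is a Safety Analysis Set of 30 to 50 subjects, the range in Section 14.3. The change is 1/n:

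- n=30: 1/30 = 3.3 percentage points.
- n=50: 1/50 = 2.0 percentage points.

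The by-subject summary counts a subject once, so this holds only if the subject has no other counted event in that row.

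**Step 4. Ceiling on the share of time before ablation**

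The inputs are the maximum consent-to-ablation interval (60 days, or 2 days under footnote 2) and follow-up to the 3-month visit, day 76 to 104 (Section 8.3). The share is interval / (interval + follow-up):

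- 60 days: 60/(60+76) = 44.1%; 60/(60+104) = 36.6%.
- 2 days: 2/(2+76) = 2.6%; 2/(2+104) = 1.9%.

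These are shares of calendar time for a subject who uses the whole interval. They are not shares of events.

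**Step 5. How likely is at least one case?**

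The documents give no rate of pre-ablation worsening. Suppose a fraction p of subjects, assumed to be 1% to 5%, worsen between consent and ablation. The chance of at least one is 1 - (1-p)^n:

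- n=30: 1 - 0.99^30 = 26%; 1 - 0.95^30 = 79%.
- n=50: 1 - 0.99^50 = 40%; 1 - 0.95^50 = 92%.

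**Step 6. Which rows are affected**

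All three of the any, serious and non-serious rows, with their by-term tables, can be affected. Section 14.4.6 counts events graded unlikely as device-related or procedure-related. A pre-ablation worsening with that grade would therefore also enter those rows; one graded not related (Section 9.2.2) would not.

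**The case against.** Several stronger readings are tempting, and the documents do not support them.

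- A reader might infer that both parts of the rule conflict with consent-onward collection. Only the onset part does.
- A reader might infer that new pre-ablation events are lost. They must be collected (8.2.1), recorded (9.3) and reported to the sponsor (9.4.1), with serious ones due within 72 hours (Table 9), and they enter the tables if they later worsen. The gap is in the summary tables. Section 14.4.6 also plans AE listings but does not say whether they go beyond its own definition.
- A reader might infer that the whole safety result is affected. Section 14.4.6 also plans device-effect summaries and device-deficiency listings. Events judged not related stay out of the device-related and procedure-related rows, while the any, serious and non-serious rows include unrelated events by design.
- A reader might take 37-44% as a bias. It is a ceiling on calendar time and falls to about 2-3% if the 48-hour footnote governs.

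It can also be argued that ablation is not the only defensible start point. Starting both parts at consent would remove the mismatch and match Sections 8.2.1, 9.1.1, 9.3 and 9.4.1. That is fair, and the plan does not label these tables as post-ablation rates. However, the Safety Analysis Set omits consented subjects in whom the device was never inserted, so consent-anchored tables would not be a complete post-consent summary either.

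Finally, no hypothesis is tested and the primary endpoint, acute procedural success, is untouched. That limits the consequence, but it does not reconcile the two start points.

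**Conclusion.** The definition is inconsistent as written, and no other section reconciles it. Under either the 60-day or the 48-hour limit, a worsening that is wholly pre-ablation is tabulated while a new, non-worsening event with the same timing is not. The practical size is unknown: the documents give neither the distribution of consent-to-ablation intervals nor a rate of pre-ablation worsening. The bounds are 3.3 or 2.0 points per affected subject, assuming 30 or 50 subjects in the Safety Analysis Set and no other counted event for that subject in the row. Pre-ablation time is at most 37-44% of the time in which worsening counts, or about 2-3% with 48 hours. Only descriptive AE rates are affected. The definition should be corrected before database lock, so that the choice cannot be seen as driven by the data.

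**What to change.** 1. Use one start point for both parts of the AE definition in Section 14.4.6. One possible wording: *onset, or an increase in severity, at or after the start of the study ablation procedure*.
2. Tabulate or list separately the events that start or worsen between consent and the start of ablation, so that nothing collected disappears from view.
3. Count an event with a missing onset date as post-ablation only if other recorded information does not place it wholly before ablation.
4. Reconcile the 60-day interval in Sections 8.1, 8.2.1 and 8.5 with the 48-hour footnote on the consent row of Tables 1 and 4.

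The cost of items 1 to 3 is a small SAP edit and one extra table or listing. AEs are already collected from consent. The existing rule already requires knowing when worsening occurred relative to consent, so the sponsor need only check that the CRF also dates it relative to ablation. Item 4 is a text correction.

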### 9.1.3. Adverse Device Effect (ADE) / Serious Adverse Device Effect (SADE)

An Adverse Device Effect (ADE) is an adverse event related to the use of the device under study.

NOTE 1: This includes any adverse event resulting from insufficiencies or inadequacies in the instructions for use, the deployment, the implantation, the installation, the operation, or any malfunction of the medical device under study.

NOTE 2: This includes any event that is a result of a use error or intentional abnormal use of the investigational device under study.

A **Serious Adverse Device Effects (SADE)** is an adverse device effect that has resulted in any of the consequences characteristic of an SAE.

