#### 9.1.4. Unanticipated (Serious) Adverse Device Effect (UADE/USADE)

An **unanticipated adverse device effect (UADE)** or **unanticipated serious adverse device effect (USADE)** is any serious adverse effect on health, safety, any life-threatening problem, or death caused by, or associated with a device, if that effect, problem, or death was not previously identified in nature, severity, or degree of incidence in the post market clinical follow up plan or risk analysis report, or any other unanticipated serious problem associated with a device that relates to rights, safety, or welfare of subjects.

Refer to Table 8 for a comprehensive list of foreseeable and anticipated adverse events.

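### Section 14.4.6 counts adverse device effects from the device-deficiency CRF, while Section 9.1.3 defines them by relatedness to the device, so the ADE and SADE tables do not count what the protocol means by those terms

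*Combined protocol and SAP*

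**What the plan says.** The protocol definition is in Section 9.1.3: "An Adverse Device Effect (ADE) is an adverse event related to the use of the device under study". The two notes under it give malfunction, inadequate instructions, operation and use error as things that are included; none is a condition. The same section says that a SADE "is an adverse device effect that has resulted in any of the consequences characteristic of an SAE". Section 9.1.4 defines the unanticipated categories separately, starting from "any serious adverse effect on health, safety, any life-threatening problem, or death caused by, or associated with a device" and adding a test of whether the effect had already been identified.

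Section 14 states that it is the statistical analysis plan. Section 14.4.6 gives the analysis rule: "An adverse device effect (ADE) is any event recorded to have led to an AE on the Investigational device deficiency CRF". It breaks ADEs down by "ADEs leading to an AE, ADEs leading to an SADE and unanticipated SADE (USADE), device, and time point during the procedure" and SADEs by "SADEs leading to an AE, SADEs leading to a USADE, device, and time point during the procedure", and plans separate ADE, SADE and USADE tables by overall incidence and by event term.

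Section 14.4.6 also plans rows taken from the AE CRF, among them device-related AEs ("defined as unlikely, possible, probable or having a causal relationship with the device"), serious device-related AEs and "Serious unanticipated device-related adverse event". It promises listings of adverse events, device effects and deficiencies.

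**The concern.** One term has two definitions that differ in source form, in unit counted and in criterion. The protocol asks whether an adverse event is related to the device. The analysis rule asks whether a deficiency record says that it led to an adverse event. An event can meet the first test and fail the second.

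Section 1.2.1 names acute safety among the main objectives, and Section 14.3 relies on 30 to 50 subjects to characterize safety. The Objectives section itself names only workflow and acute performance, and Section 3.2.2 places adverse events among the additional endpoints. What is at stake is whether a reader of the ADE and SADE tables can take the labels at their protocol meaning. At this sample size a difference of one subject is visible.

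**Working it through.** The documents state no figure that depends on this definition, so there is none to reproduce. The check compares the texts and then gives the scale.

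**1. What creates each record.** Section 9.2.2 has the clinician grade device causality for all collected AEs, without reference to a deficiency. Section 9.1.5 ties the deficiency record to a device failure that is detected or suspected. Nothing requires a deficiency record for each device-related AE.

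**2. Events outside the analysis rule.** Take an AE graded causal for the device, with no failure detected or suspected. It is an ADE under Section 9.1.3. It is not one under Section 14.4.6, because no deficiency record points to it. If it is serious, it is also a SADE under Section 9.1.3 and is missing from the SADE table. For USADE this is an inference only, because Section 9.1.4 does not define that term through ADE.

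**3. Events counted more than once.** Section 14.4.6 counts events on the deficiency CRF. If two deficiencies are each recorded as having led to the same AE (assumed), a by-event count gives 2 where Section 9.1.3 gives 1. A by-subject count is not raised in this way.

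**4. The breakdown lines.** Under Section 9.1.3 an ADE is itself an AE, so asking which ADEs led to an AE has no meaning. Under the Section 14.4.6 rule the answer is all of them, and the same holds for SADEs. The lines are informative under neither definition. They make sense if ADE stands for a deficiency.

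**5. Scale.** Section 14.4.1 bases AE and device-effect percentages on the whole analysis population. Take N = 30 and N = 50, the planned minimum and maximum. If k subjects have a device-related AE but no linked deficiency record, the by-subject ADE incidence is low by k/N. The value of k is assumed.

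| k | N = 30 | N = 50 |
|---|---|---|
| 0 | 0 | 0 |
| 1 | 1/30 = 3.3 points | 1/50 = 2.0 points |
| 2 | 2/30 = 6.7 points | 2/50 = 4.0 points |
| 3 | 3/30 = 10.0 points | 3/50 = 6.0 points |

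**6. Disagreement within one report.** Assume two subjects with SAEs graded causal for the device, one of them with a linked deficiency record. At N = 30 the SADE table shows 1/30 (3.3%) and the serious device-related AE row shows 2/30 (6.7%). At N = 50 the figures are 1/50 (2.0%) and 2/50 (4.0%). Under Section 9.1.3 a SADE is a serious device-related AE, so the two should agree.

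**The case against.** The strongest reply is that little depends on these tables. The analysis is descriptive, the primary endpoint is entrance block, and reporting to the sponsor and regulator follows Section 9, not the table rule. The device-related rows and the listings still hold every event. All of this stands. A reader might infer that safety events disappear from the report, or that expedited reporting is weakened; the documents support neither.

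A reader might also infer that the tables must understate device effects. They need not. Section 9.1.5 defines failure broadly, including failure to meet the investigator's expectations on safety or performance, so some events without a malfunction may reach the deficiency CRF. The CRF is not shown, and by-event counts can move upward (step 3).

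The collection schedule invites another strong reading. Footnote 4 of Table 4 schedules deficiency collection at ablation and pre-discharge only, while AEs are also collected at day 7 and month 3. This may make a missing link likelier for a late event. It does not show that late events cannot be linked, since Section 9.1.5 and Table 9 allow a failure to be reported at any time and a late AE can be tied to an earlier deficiency.

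Finally, the device-related rows are an imperfect yardstick. They count AEs graded unlikely, a category that Section 9.2.2 describes as having no apparent relevance to the device, and Section 9.1.3 does not say which grades qualify as related. Some disagreement could therefore arise even with complete linkage. The example in step 6 avoids this by using events graded causal. The difference between the definitions remains after all these points.

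**Conclusion.** The concern holds as a conflict of definitions. Followed as written, Section 14.4.6 produces ADE and SADE tables that do not match Section 9.1.3, and by inference a USADE table that may not match Section 9.1.4. The labels are wrong as written, whatever the data turn out to be.

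The numerical effect is unknown and may be nil. It is 3.3 points (N = 30) or 2.0 points (N = 50) per affected subject on by-subject incidence, with a possible excess on by-event counts. These figures rest on assumed numbers of unlinked events. Confidence is high for the mismatch and does not extend to its size. It should be corrected before the tables are produced.

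**What to change.** In Section 14.4.6:

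- Derive ADE and SADE from the AE CRF, using device causality and seriousness as in Sections 9.1.2 and 9.1.3, whether or not a deficiency record exists.
- Derive USADE by adding the Section 9.1.4 test that the effect was not already identified in kind, severity or frequency. Causality and seriousness alone cannot identify a USADE.
- State one causality cut-off and use it for these tables and for the device-related AE rows. Do not simply carry over the rows' present cut-off, because it would bring AEs graded unlikely into the ADE and SADE tables.
- State whether the investigator's or the sponsor's causality assessment governs the tables, since Section 9.4.1 foresees disagreement between them.
- Tabulate device deficiencies separately under that name, including those that led to an AE, a SADE or a USADE, and keep the breakdowns by device and by procedural time point there.
- Delete the lines for ADEs and for SADEs that led to an AE.

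The cost is SAP wording and table shells. Causality is already graded for all collected AEs (Section 9.2.2), the sponsor already documents seriousness and device relationship (Section 9.4.1), and a row for serious unanticipated device-related AEs is already planned. No new data collection is needed.
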